OTC Over the Counter

PGIS Patient Global Impression of Severity PGIC Patient Global Impression of Change

PP Per Protocol

PRO Patient Reported Outcome RLD Reference Listed Drug SAE Serious Adverse Event

US United States
UV Unscheduled Visit

26Apr2019 Protocol: **HDCS 1701** Page 5 of 67 Version 4.0

1 TITLE:

A randomized, double-blind, placebo-controlled, multicenter, parallel group pilot study of the safety and efficacy of Hydrocortisone Acetate Suppositories, 25 mg compared to placebo suppositories in the treatment of symptomatic internal hemorrhoids.

2. INTRODUCTION:

Hemorrhoidal disease is common in the United States with at least 15 million people comprising nearly 5% of the population suffering from this condition. Hemorrhoids begin with the enlargement of normal vascular cushions which are present in the anal canal at birth and are themselves a normal part of the human anatomy. However, hemorrhoids may be diagnosed only if symptoms of bleeding, prolapse or thrombosis exist in addition to the presence of enlarged vascular cushions. Hemorrhoids may be internal and/or external. Internal hemorrhoids occur above the dentate line and are covered with colonic mucosa whereas external hemorrhoids occur below the dentate line and are covered with squamous epithelium. The incidence of hemorrhoids peaks in the 65-74-year-old age group with lesser rates for both younger and older age groups.

Current theory attributes the development of hemorrhoids to the dilation of the vascular cushions due to increased anal sphincter pressure which interferes with the drainage of blood from the rich plexus of arterial and venous vessels in these cushions but does not interfere with the in-flow of blood through the arteries. This results in dilation and progressive development of hemorrhoids. A major factor contributing to hemorrhoidal development is the gradual degeneration of the connective tissue in the vascular cushions which leads to further enlargement of the vessels and to their eventual prolapse. This combination of decreased outflow and gradual connective tissue degeneration results in the progressive development of the condition.

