This study will be a randomized, double-blind, placebo-controlled, multicenter, parallel group pilot study of 25 mg hydrocortisone suppositories administered twice daily compared to a vehicle placebo in subjects with symptomatic internal hemorrhoids. Approximately 100 subjects will be randomized in a 1:1 ratio (Test product: placebo).

The study will consist of 3 periods:

- a. Screening Period (2 weeks/Days -14 to -1)
- b. Treatment Period (2 weeks/ Days 1-14)
- c. Follow-up Period (2 weeks/ Days 15-29)

Subjects will use daily paper diaries to record the time and date of each medication application, concomitant medication and adverse events (AEs). The subjects will use electronic diaries to complete the Internal Hemorrhoids Sign and Symptom Assessment (IHSSA) daily for the duration of the study and the Patient Global Impression of Severity (PGIS) and Change (PGIC) at visits.

6. STUDY POPULATION:

Male and female subjects, at least 18 years of age, with a diagnosis of symptomatic internal hemorrhoids will be selected to participate in the study.

7. PRODUCT DESCRIPTION:

Test Product: Hydrocortisone Acetate Suppository, 25 mg (Nivagen Pharmaceuticals Inc.) Placebo: Vehicle Suppository (Nivagen Pharmaceuticals Inc.)

8. GROUPS:

Two Groups (1:1) Total Subjects: Approximately 100 (50:50)

9. STUDY SCHEDULE:

Visit 1 (Days -14±2; Initiation of Screening)

Visit 2 (Day 1; Start of Treatment)

Visit 3 (Day 8±1, Interim)

Visit 4 (Day 15±2, End of Treatment)

Visit 5 (Day 29±3, Follow-Up/End of Study; UV/ED)

26Apr2019 Protocol: **HDCS 1701** Page 7 of 67 Version 4.0

10. STUDY OUTLINE:

Visit Title	Initiation of Screening	Start of Treatment	Interim	End of Treatment	Follow-up/End of Study UV/ED ⁸
Visit Number	Visit 1	Visit 2	Visit 3	Visit 4	Visit 5
Study Day	Day -14±2	Day 1	Day 8±1	Day 15±2	Day 29±3
Informed Consent	X				,
Medical History	X				
Demographics	X				
Concomitant Medication	37	37	37	37	37
Review	X	X	X	X	X
Physical Exam including Vital Signs	X				
Clinical Laboratory Tests	X ¹		X^2	X^3	
Urine Pregnancy Test ⁴	X	X	X	X	X
Urine Drug Screen	X				
Breath Alcohol Test	X				
Inclusion/Exclusion Criteria	X	X			
Adverse Events Assessment		X	X	X	X
Anoscopy		X		X	
Assessment of Disease Grade/ Diagnosis		X			
Randomization		X			
Cognitive Interview ⁵	X				
Exit Interview ⁶				X	
PROMIS Global Health		37			
Questionnaire		X		X	
IHSSA daily diary ⁷ (ePRO)	X	X	X	X	X
Patient Global Impression of Severity (PGIS) (ePRO)		X		X	

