Patient Global Impression of Change (PGIC) (ePRO)				X	
Dispense IP Supplies		X			
IP Accountability				X	X as needed
Drug will be returned Dispense Diary/Instructions	X	X	+	X	
Subject Compliance/Diary	Λ		+		
Review and Collection		X		X	X as needed
Schedule Next Visit	X	X	X		X as needed

¹Complete blood count (CBC), comprehensive metabolic panel (CMP), urinalysis, HIV, Hepatitis B, Hepatitis C ²Comprehensive metabolic panel (CMP)

Protocol: HDCS 1701 Page 8 of 67 26Apr2019 Version 4.0

³Complete blood count (CBC), comprehensive metabolic panel (CMP)

⁴The urine pregnancy test is to be conducted for women of child-bearing potential. Tubal ligation is not considered equivalent to female sterilization. Women with a history of tubal ligation are still considered females able to become pregnant and must complete a urine pregnancy

⁵First 5 enrolled subjects at a sponsor selected site ⁶First 25 enrolled subjects who reach Visit 4 and agree to participate in the interview

⁷Internal Hemorrhoids Sign and Symptom Assessment. To be completed daily throughout the study via electronic diary (ePRO). ⁸UV, Unscheduled Visit; ED, Early Discontinuation Visit

11. RANDOMIZATION:

- a. Two groups.
- b. This is a double-blind study.
- c. An independent third party will generate and hold the randomization code throughout the conduct of the study. The Nivagen product and placebo will be similar in appearance and will also be labelled and packaged to be similar in appearance. The Subject and Investigator will be blinded as to the treatment

12. INCLUSION CRITERIA:

- a. Subject reports an average score of 1.5 or greater (on 0-4 scale) on either the IHSSA itch severity or itch frequency items (Section 21.b) during the 2-week screening period
- b. Subject reports hemorrhoidal bleeding associated with their bowel movements at least 50% of the days where a bowel movement occurs, as indicated by responses to the IHSSA (Section 21.b) during the 2-week screening period.
- c. Have a diagnosis of symptomatic Grade I, II or III internal hemorrhoids (Banov et al. 1985) by history; confirmed by anoscopy.
- d. Is a male or female aged 18 years and older.
- e. Give voluntary consent to participate in the study following a full explanation of the nature and purpose of the study, by signing the IRB-approved Informed Consent document prior to any study specific evaluations.

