- f. Is willing to forego the use of non-prescription (OTC) and prescription medication or procedures for the treatment of hemorrhoidal disease and/or pain for the duration of the study.
- g. Female Subjects of childbearing potential (excluding women who are or premenarchal, surgically sterilized (by hysterectomy) or postmenopausal for at least 1 year), in addition to having a negative urine pregnancy test, must be willing to use an acceptable form of birth control during the study from the day of the first dose administration to 30 days after the last administration of study drug. For this study, the following are considered acceptable methods of birth control: oral or injectable contraceptives, contraceptive patches, Depo-Provera® (stabilized for at least 3 months), NuvaRing® (vaginal contraceptive), ImplanonTM (contraceptive implant), double barrier methods (e.g. condom and spermicide), IUD, tubal ligation, Essure or abstinence with a 2nd acceptable method of birth control should the Subject become sexually active. Subjects on hormonal contraception must be stabilized on the same type for at least three months prior to enrollment in the study and must not change the method during the study. A sterile sexual partner is NOT considered an adequate form of birth control.
- h. All male Subjects must agree to use accepted methods of birth control with their partners, from the day of the first dose administration to 30 days after the last administration of study drug. Abstinence is an acceptable method of birth control. Female partners should use an acceptable method of birth control as described in the above Item g.
- i. Subjects agree to not appreciably change their diet during the study.

26Apr2019 Protocol: **HDCS 1701** Page 9 of 67 Version 4.0

13. EXCLUSION CRITERIA:

- a. Has a fissure or a fistula-in-ano, abscess, polyps or colorectal adenoma or colorectal cancer, arteriovenous malformations, or any other pathological condition of the anus other than symptomatic internal hemorrhoids which might be a potential cause of hematochezia.
- b. Has inflammatory bowel disease.
- c. Has Grade IV hemorrhoidal disease (Banov et al. 1985).
- d Has external hemorrhoids
- e. Has had or is receiving pelvic radiation.
- f. Is using other OTC, prescription or narcotic medications for treatment of hemorrhoidal disease and/or pain. Washout of 7 days required if medicated treatment used.

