- g. Has had a sphincterotomy, anal stretch or other procedure that may reduce the resting anal pressure.
- h. Endoscopic or surgical treatment of internal hemorrhoids in the past such as IRC, rubber band ligation or injection therapy.
- i. Is immunocompromised (e.g. receiving cancer chemotherapy, steroids, HIV positive).
- j. Is a pregnant or nursing female.
- k. Is known to be allergic to latex, lanolin, white petrolatum, paraffin wax, sorbitan sesquioleate, propylene glycol, hydrocortisone or psyllium.
- 1. Is not willing to use a finger to insert the suppository even with a finger cot.
- m. Has received glucocorticoids (any form) within the last 2 months prior to starting study.
- Subjects who have unstable medical disorders that are clinically significant or have lifethreatening diseases.
- o. Subjects who consume excessive amounts of alcohol (greater than two drinks per day) or use drugs of abuse (including, but not limited to, cannabinoids, cocaine and barbiturates).
- p. Positive urine screening for drugs of abuse or positive alcohol breath test.
- q. Subjects who have participated in an investigational drug study (i.e., Subjects have been treated with an investigational drug) within 30 days prior to baseline will be excluded from study participation. Subjects who are participating in non-treatment studies such as observational studies or registry studies can be considered for inclusion.
- r. Subjects who have been previously enrolled in this study.
- s. A subject who has a history of being unresponsive to anal hydrocortisone therapy.
- t. Lacks suitability for participation in this study for any reason in the opinion of the Investigator.
- u. Clinically significant complete blood count (CBC), comprehensive metabolic panel (CMP), urinallysis or positive HIV, Hepatitis B, Hepatitis C.
- v. Female subjects with Abnormal Uterine Bleeding (menorrhagia).

14. TREATMENTS:

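### Item 12.g starts the contraception duty on the day of the first dose, so a woman newly starting a non-hormonal method has no stated duty during the 12 to 16 days of screening (minor, cheap to close)

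*Combined protocol and SAP*

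**What the plan says.** Section 12, item g asks a woman of childbearing potential for a negative urine pregnancy test and for willingness to use an accepted method "during the study from the day of the first dose administration to 30 days after the last administration of study drug". Only hormonal methods carry a requirement that reaches back before entry: "Subjects on hormonal contraception must be stabilized on the same type for at least three months prior to enrollment in the study". The non-hormonal options (double barrier, IUD, tubal ligation, Essure, abstinence with a backup method) have no lead-in. Women who are "surgically sterilized (by hysterectomy) or postmenopausal for at least 1 year" fall outside the item.

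Section 28 schedules Visit 2 (Day 1) 14±2 days after Visit 1, and the first suppository is used at home after Visit 2. Urine pregnancy tests are planned at all five visits (Sections 10 and 28).

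Section 13, item j lists as an exclusion "Is a pregnant or nursing female". Section 19 makes pregnancy a reason for discontinuation. Section 24, item h requires it to be reported within 24 hours and followed to outcome, because the embryo or fetus may have been exposed.

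**The concern.** The opening words of the duty might seem to cover the whole study, but the clause that follows limits them to the period from the first dose. Screening is therefore outside the duty, and no other visible section fills the gap for a woman who begins a non-hormonal method on joining the study.

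At stake is an early pregnancy, begun in screening, that item 13.j means to exclude but that is not yet detectable at Visit 2. It would be dosed until a later test found it. The plan treats such exposure as a concern on its own terms, through the exclusion and the pregnancy follow-up, and Section 22.a acknowledges systemic absorption of topical corticosteroids. The three-month rule shows that the plan already places contraception requirements before dosing, but for one class of method only.

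**Working it through.** The plan states no figure for this point, so there is none to reproduce. The check compares the sections and then does calendar arithmetic.

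**Who is left without a duty**

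- Hormonal users: covered before entry by the three-month rule in 12.g.
- Women with an IUD, tubal ligation or Essure already in place: no stated duty in screening, but protected in practice.
- Women newly starting double barrier, abstinence or a new IUD: no duty until the day of the first dose.

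**Length of the interval** (Section 28, Visit 1, item 13)

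- Shortest: 14 − 2 = 12 days.
- Longest: 14 + 2 = 16 days.
- With the duty starting at Visit 1: 0 days.

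**What the existing checks reach**

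- The Visit 1 and Visit 2 tests come before dosing. The Visit 2 test is the last of these and finds only what is detectable on that day.
- The tests at Visits 3, 4 and 5 come after dosing has begun. They limit exposure but cannot prevent it.

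**Doses taken before the next test, if Visit 2 misses a pregnancy**

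Inputs: twice-daily dosing (Section 14), first dose at home after Visit 2 and 28 suppositories dispensed (Section 28), Visit 3 on Day 8±1. Assumptions: full adherence and a first dose on Day 1.

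For a visit on Day d:

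doses = Day 1 (1 or 2) + 2 × (d − 2) + morning of the visit (0 or 1)

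- d = 7: 1 + 10 + 0 = 11, up to 2 + 10 + 1 = 13
- d = 8: 1 + 12 + 0 = 13, up to 2 + 12 + 1 = 15
- d = 9: 1 + 14 + 0 = 15, up to 2 + 14 + 1 = 17

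The overall range before the Visit 3 test is 11 to 17. If Visit 3 also missed it, the same count for Visit 4 on Days 13 to 17 starts at 1 + 22 + 0 = 23 and is capped at the 28 dispensed, so 23 to 28. These counts are conditional on a missed pregnancy and say nothing about how likely a miss is.

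**Size of the group**

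No case count can be derived. About 100 people of both sexes are randomized (Section 5), and Section 2 states: "The incidence of hemorrhoids peaks in the 65-74-year-old age group with lesser rates for both younger and older age groups". Postmenopausal women and hormonal users drop out of the affected group. Under 1:1 allocation, on average half of any such women would receive the placebo vehicle.

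**The case against.** The strongest case against is that tying the duty to drug exposure is coherent. No study drug is given in screening, and item 12.h for men uses the same start. Pregnancy is tested twice before dosing and three times afterwards, pregnant women are excluded, and a pregnancy leads to discontinuation, reporting and follow-up. Eligibility is reviewed at Visits 1 and 2, and item 13.t lets the investigator exclude a woman who "Lacks suitability for participation in this study for any reason in the opinion of the Investigator". Harm requires a miss at Visit 2, which depends on a detection lag the documents do not give. The consent form was not available for this review and may already carry the advice.

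Most of this stands, and it keeps the point minor. It does not close the gap. Item 13.t sets no contraception rule and cannot act on a pregnancy nobody has recognised, and the later tests follow the first doses. The fix does not depend on knowing the lag: for any positive lag, an earlier start lowers the chance that a pregnancy passes Visit 2 undetected, provided the women comply.

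A reader might infer two stronger things that the documents do not support. One is that the schedule fixes how old an undetected pregnancy could be at Visit 2, with and without the change. That would need conception to fall on the day of intercourse; the schedule fixes only the interval between visits. The other is that Visit 2 should be booked no earlier than 14 days after Visit 1 for new starters. Such a cut-off would rest on the missing detection lag.

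**Conclusion.** The point holds as a minor safety improvement. Item 12.g leaves 12 to 16 days of screening without a stated contraception duty for a woman newly starting a non-hormonal method. Confidence is high in that reading of the text. It is lower on whether participants face a gap in practice, because the consent form may already fill it.

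The risk is not quantified, since neither the test's detection lag nor any fetal risk from this product is given, and the affected group is likely very small. The smallness is itself an inference from the sample size and a general statement on age, not from an expected trial mix. The dose range of 11 to 17 before Visit 3 rests on full adherence and a first dose on Day 1.

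It would go too far to read this as a contradiction in the plan or as a lack of pregnancy safeguards. No endpoint or analysis is touched.

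**What to change.** In item 12.g, replace the phrase that starts the duty on the first-dose day with *from Visit 1 (signing of informed consent)*. Keep the 30-day end and the Visit 2 urine test. Align the consent form if it does not already say this. Item 12.h can stay as it is, and the visit windows need no change.

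The change adds no visit, test or staff. Its burden is 12 to 16 more days of contraception for some women. That includes some who then fail item 12.a, or item 12.b ("Subject reports hemorrhoidal bleeding associated with their bowel movements at least 50% of the days where a bowel movement occurs"), both judged over the two-week screening period, and so are never dosed. The duty would still rest on stated willingness, and a small window could remain if the true detection lag exceeds the interval between Visits 1 and 2.
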